9.3.2. Unsolicited Adverse Events

When calculating the incidence of unsolicited AEs (i.e., on a per subject basis), each subject will only be counted once at the highest severity and/or relationship, and any repetitions of AEs within a subject will be ignored; the denominator will be the total number of subjects in the safety population. All AEs reported will be included in the summaries and analyses.

The number and percentage of subjects reporting at least one unsolicited AE will be summarized by MedDRA system organ class and preferred term. A 95% CI will be presented for the percentage of subjects reporting any unsolicited AE (serious or non-serious) for each MedDRA system organ class and preferred term over all study vaccinations ([Table 97](#)).

The following summaries for unsolicited AEs will be presented by MedDRA system organ class, preferred term, and study group:

- Incidence of AEs by severity and relationship to study product ([Table 98](#), [Table 99](#));
- Incidence of non-serious, related AEs by severity ([Table 100](#), [Table 101](#));
- Incidence of AEs over time (Days 1-8, Days 9-22 post each study vaccination) ([Table 102](#));
- Incidence of non-serious, related AEs over time (Days 1-8, Days 9-22 post each study vaccination) ([Table 103](#)) – note this table presents results for secondary safety endpoint, “Occurrence of study vaccine-related unsolicited non-serious AEs from the time of each study vaccination through approximately 21 days after each study vaccination”;
- Total frequency of AEs over time (Days 1-8, Day 9 through approximately Day22 post each study vaccination) ([Table 104](#), [Table 105](#));
- Subject listing of non-serious AEs of moderate or greater severity ([Table 110](#));
- Bar chart displaying total frequency of AEs by severity and MedDRA system organ class and study group ([Figure 28](#), [Figure 29](#));
- Bar chart displaying incidence of AEs by severity and MedDRA system organ class, and study group ([Figure 30](#), [Figure 31](#));
- Bar chart displaying total frequency and incidence of AEs by relationship to study product, MedDRA system organ class, and study group ([Figure 32](#), [Figure 33](#), [Figure 34](#), [Figure 35](#)).

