8.2.12 Clinic Visit, All Treatment Arms

Visit 11, Day 43 (Window: Day 22+7 days post second study vaccination), Treatment Arms 1 and 4

Visit 13, Day 142 (Window: Day 22+7 days post second study vaccination), Treatment Arms 2, 3, 5, and 6

- Interim medical history, including an assessment for new medical conditions, stability of chronic diseases and symptoms suggestive of PIMMCs, will be obtained by interview of subjects and any changes since the previous clinic visit or phone call will be noted.
- All concomitant medications (including solicitation for receipt of any non-study influenza vaccines) will be recorded on the appropriate DCF.

- All AE/SAEs will be recorded on the appropriate DCF. Note: AEs will be limited to SAEs and MAAEs, including NOCMCs and PIMMCs, for subjects who are discontinued from receipt of the second study vaccination and being followed for safety.
- A targeted physical examination, including an assessment for signs suggestive of PIMMCs, may be performed, if indicated based on review of interim medical history, by a study clinician licensed to make medical diagnoses and listed on the Form FDA 1572 as the site PI or sub-investigator.
- Approximately 15 mL of venous blood will be collected for serological assays.
- Approximately 16 mL of venous blood will be collected for future research.

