11.4.2 Subject Enrollment and Follow-up

Based on the accrual rates observed in similar studies, it seems reasonable to expect that the participating VTEUs will be able to enroll this trial in a timely fashion. In previous DMID trials, 7 VTEUs recruited 388 healthy subjects, 19 to 64 years of age, in 14 weeks. Prior experience suggests up to 15% of subjects (approximately 10% of subjects assigned to the 4-month interval and 5% of subjects assigned to the 21-day interval), 19 to 64 years of age, may be excluded from the per protocol (PP) analysis for the primary immunogenicity outcome either because they did not receive the second study vaccination, were lost-to-follow-up, or because they had a protocol deviation requiring their exclusion from the PP analysis.

Follow-up will consist of 2 segments. The first encompasses the core data for this trial and will consist of results for all study visits through approximately 21 days after the last study vaccination. The second segment consists of a 6-month immunogenicity assessment and follow-up safety assessments through approximately 12 months after the last study vaccination.

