6.3. Analysis Populations

6.3.1. Safety Population

The Safety Analysis population includes all subjects who received at least one study vaccination.

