9.3.1. Solicited Events and Symptoms

Systemic solicited adverse events were collected pre-vaccination, and systemic and local solicited adverse events were collected at-least 20 minutes post-vaccination and then daily for 7 days after each vaccination and graded on a scale of 0 (absent), 1 (mild), 2 (moderate) and 3 (severe). Systemic events include fever, feverishness, fatigue, malaise, myalgia, arthralgia, headache, and nausea. The grading scale for systemic events, including quantitative grading for fever, is included in [Table 11](#). Local events include pruritus, ecchymosis, erythema, induration/swelling, pain, and tenderness. Ecchymosis, erythema, and induration are measured by both functional and measurement grading scales as defined in [Table 10](#).

When calculating the incidence of solicited events, each subject will be counted once at the highest severity following the applicable vaccination, and any repetitions will be ignored. For summaries presented separately for each vaccination, the denominator for percentages will be the number of subjects who received the respective vaccination with non-missing data for the event summarized. For summaries over all vaccinations the denominator will be the number of subjects who received at least one vaccination with non-missing data for the event summarized.

The number and percentage of subjects reporting at least one solicited adverse event of each severity will be summarized for each solicited symptom, any systemic symptom, any local symptom, and any symptoms. For each event the denominator is the number of subjects who received the applicable vaccination with non-missing data for the specific event. The 95% CI calculated using Clopper-Pearson methodology from a binomial distribution (SAS Proc Freq with a binomial option) will be presented ([Table 84](#), [Table 85](#), [Table 86](#)). Logistic regression models will be fit to estimate the effect of prime-boost combination (*PrimeBoost*), Boost dose (*BoostDose*), and interval between vaccinations (*Interval*) on the probability of reporting any local event or reporting any systemic event after either vaccination ([Table 87](#), [Table 88](#)). If statistically significant effects are observed in the model for local events or systemic events, then additional models will be fit for each individual event of that type.

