| | n | % (95% CI) | n | % (95% CI) | n | % (95% CI) | n | % (95% CI) | n | % (95% CI) | n | % (95% CI) | n | % (95% CI) |
| N = Number of subjects in the Safety Population who received any study vaccination; n = Number of subjects reporting event 95% CI estimated using the Clopper-Pearson exact method | | | | | | | | | | | | | | |

Tables with similar format:

Table 85: Number and Percentage of Subjects Experiencing Solicited Events with 95% Confidence Intervals by Symptom and Study Group (Safety Population) – Post Study Vaccination 1

[Footnote update] N = Number of subjects in the Safety Population who received the first study vaccination.

Table 86: Number and Percentage of Subjects Experiencing Solicited Events with 95% Confidence Intervals by Symptom and Study Group (Safety Population) – Post Study Vaccination 2

[Footnote update] N = Number of subjects in the Safety Population who received the second study vaccination.

Table 87: Logistic Regression Model to Evaluate the Relationship of Study Vaccination with Reporting Any Local Event Post Second Study Vaccination, Safety Population

[Implementation Note: If statistically significant effects (defined as p-value <0.05) are observed in the model for local events then this table should be repeated for additional models which will be fit for each individual local event. Any solicited local event grade 1 or higher reported within 7 days of study vaccination will count as a reported event.]

| Model Parameter | Parameter Category | Parameter Estimate | SE | p-value | Odds Ratio | 95%CI |
|-----------------|------------------------|--------------------|-------|---------|------------|-----------|
| Intercept | N/A | xxx.x | xxx.x | x.xxx | - | - |
| Prime-boost | Homologous (reference) | - | - | - | - | - |
| | Heterologous | xxx.x | xxx.x | x.xxx | xx.x | xx.x-xx.x |
| Boost Dose | 15 mcg (reference) | - | - | - | - | - |
| | 3.75 mcg + AS03 | xxx.x | xxx.x | x.xxx | xx.x | xx.x-xx.x |
| Interval | 21 days (reference) | - | - | - | - | - |
| | 120 days | xxx.x | xxx.x | x.xxx | xx.x | xx.x-xx.x |

N = XX (number of subjects in the Safety Population)

Table with similar format:

Table 88: Logistic Regression Model to Evaluate the Relationship of Study Vaccination with Reporting Any Systemic Event Post Second Study Vaccination, Safety Population

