Table 101: Number and Percentage of Subjects Experiencing Non-Serious Related Unsolicited Adverse Events Within 21 Days Post Study Vaccination by MedDRA® System Organ Class and Preferred Term, Maximum Severity, and Study Group, Safety Population

[Implementation Note: If an SOC has only one PT reported, the ‘Any PT’ row will be omitted. Only the SOC/PT with >= 1 event reported will be shown for each group. Events through 'Day 22' include events through the study visit planned for 21 days post the relevant vaccination. If that visit is missed, then a cutoff of exactly 21 days post vaccination will be used.]

Table 102: Number and Percentage of Subjects Experiencing Unsolicited Adverse Events Within 21 Days Post Study Vaccination by MedDRA® System Organ Class and Preferred Term, Day Post Study Vaccination, and Study Group, Safety Population

| MedDRA® System Organ Class | MedDRA® Preferred Term | Post Vaccination 1 | | | | | | Post Vaccination 2 | | | | | | Post Any Vaccination | |
|--|------------------------|--------------------|----|----------|----|----------|----|--------------------|----|----------|----|----------|----|----------------------|----|
| | | Day 1-8 | | Day 9-22 | | Day 1-22 | | Day 1-8 | | Day 9-22 | | Day 1-22 | | Day 1-22 | |
| | | n | % | n | % | n | % | n | % | n | % | n | % | n | % |
| Group 1: 2013 3.75+AS03/ 2017 3.75+AS03 (D1-D22) (N=X) | | | | | | | | | | | | | | | |
| Any SOC | Any PT | x | xx | x | xx | x | xx | x | xx | x | xx | x | xx | x | xx |
| [SOC 1] | Any PT | | | | | | | | | | | | | | |
| | [PT 1] | | | | | | | | | | | | | | |
| | [PT 2] | | | | | | | | | | | | | | |
| [SOC 2] | Any PT | | | | | | | | | | | | | | |
| | [PT 1] | | | | | | | | | | | | | | |
| | [PT 2] | | | | | | | | | | | | | | |
| [Repeat for all study groups & All Subjects] | | | | | | | | | | | | | | | |
| N = Number of subjects in the Safety Population. This table presents number and percentage of subjects. For each time period, a subject is only counted once per PT. | | | | | | | | | | | | | | | |

[Implementation Note: If an SOC has only one PT reported, the ‘Any PT’ row will be omitted. Only the SOC/PT with >= 1 event reported will be shown for each group. Events through 'Day 22' include events through the study visit planned for 21 days post the relevant vaccination. If that visit is missed, then a cutoff of exactly 21 days post vaccination will be used.]

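### Post-dose-2 unsolicited AE percentages are divided by the whole Safety Population, including subjects who never received dose 2, whereas the solicited-event tables use recipients of the respective dose

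*SAP*

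**What the plan says.** SAP 9.3.2 sets a single denominator for unsolicited AE incidence: "the denominator will be the total number of subjects in the safety population". SAP 6.3.1 defines that population: "The Safety Analysis population includes all subjects who received at least one study vaccination". Receipt of dose 2 is not required.

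The shells of Tables 102 and 103 have separate Post Vaccination 1, Post Vaccination 2 and Post Any Vaccination columns, each with n and a percentage. Both footnotes read "N = Number of subjects in the Safety Population. This table presents number and percentage of subjects", with no restriction by dose. SAP 9.3.2 identifies Table 103 as the display for a secondary safety endpoint. Figure 30 is to be drawn as one file per vaccination plus one for all vaccinations. It plots percentages of subjects, and its panel N is again the Safety Population. Figure 31 follows the same format.

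For solicited events the rule is different. SAP 9.3.1 states that, for summaries by vaccination, "the denominator for percentages will be the number of subjects who received the respective vaccination with non-missing data for the event summarized". The footnote to Table 86, the post-dose-2 solicited table, reads "N = Number of subjects in the Safety Population who received the second study vaccination".

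**The concern.** The protocol defines the secondary endpoint as unsolicited non-serious AEs from each vaccination to about 21 days after it. For the second window, the subjects at risk are those who received the second dose. Under the SAP rule, a subject who stops after dose 1 stays in the Post Vaccination 2 denominator but cannot enter the numerator.

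Two things follow. The post-dose-2 percentage is too low as an incidence among dose-2 recipients. A reader who sets solicited beside unsolicited post-dose-2 figures for the same arm, or dose 1 beside dose 2 in Table 102, is also comparing percentages on different bases without being told.

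**Working it through.** **Inputs**
- Arm size: 30 (Protocol 11.4.3; SAP Section 5).
- Denominators: as set out in SAP 9.3.2, SAP 9.3.1 and the table footnotes.
- Share of an arm without dose 2, written d: not given in either document. The nearest figures are the expected exclusions from the per-protocol analysis in Protocol 11.4.2: "approximately 10% of subjects assigned to the 4-month interval and 5% of subjects assigned to the 21-day interval". That sentence pools three reasons: no second vaccination, loss to follow-up, and a protocol deviation. As planning figures they are therefore a ceiling for d.
- True post-dose-2 incidence among recipients, written p: not given. I assume 10%, 20%, 30% and 50% to show a range.

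**The plan's own figure.** 30 × (1 − 0.10) = 27, which matches N=27 in Protocol Table 14 and SAP Table 8. The same step for the 21-day arms gives 30 × (1 − 0.05) = 28.5.

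**Formula.** Let x be the number of subjects with a post-dose-2 event and N2 the number who received dose 2, in an arm where all 30 received dose 1.

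reported = x/30 = (x/N2) × (N2/30) = p × (1 − d)

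The relative understatement is exactly d, whatever the value of p.

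**Results at the planning ceiling**

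| Assumed true p | 4-month arms (d = 0.10) | 21-day arms (d = 0.05) | Shortfall, points (4-month / 21-day) |
|---|---|---|---|
| 10% | 9.0% | 9.5% | 1.0 / 0.5 |
| 20% | 18.0% | 19.0% | 2.0 / 1.0 |
| 30% | 27.0% | 28.5% | 3.0 / 1.5 |
| 50% | 45.0% | 47.5% | 5.0 / 2.5 |

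**Range for d.** At d = 0 the factor is 1.00 and nothing is lost. At d = 0.15 it is 0.85, so a true 30% would print as 25.5%. I include 15% because the same protocol sentence gives up to 15% as its overall figure. The interval-specific figures average only (4 × 10% + 2 × 5%)/6 = 8.3% over the six arms.

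**Whole-number example.** Take six subjects with an event in a 4-month arm where 27 received dose 2. Among recipients this is 6/27 = 22.2% (exact 95% CI 8.6 to 42.3). The plan would print 6/30 = 20.0% (7.7 to 38.6).

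**Between intervals, conditional on the ceiling.** If d really were 0.10 and 0.05, equal true rates would give a 4-month to 21-day ratio of 0.90/0.95 = 0.947.

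**The case against.** The best defence is that this matters little and can be undone from planned outputs. Tables 102-103 print n beside each percentage, and Table 16 gives the number receiving vaccination 2 by group, so a reader can recompute the percentage for the any-event row or any other. The two tables are not in the topline set, and their shells carry no interval or test. The planned dose-1 versus dose-2 comparison by McNemar's test concerns solicited events in recipients of both doses and is unaffected. The study is descriptive, and the shortfall is small beside the confidence intervals at 30 per arm. All of this stands. It limits the importance of the point but does not make the denominator right.

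The general statement in SAP Section 9, that percentages may rest on non-missing observations or on a population and that each table will say which, does not help. These tables do say which, and they name the Safety Population.

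Three stronger readings are tempting, and the documents support none of them:

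- *A reader might infer that the rule flatters the 4-month interval.* That holds only if more second doses are missed in those arms. Protocol 11.4.2 gives pooled exclusions, not missed doses, so the difference by interval is conditional.
- *A reader might infer selective loss by interval from the bar on dose 2 after a Grade 3 event.* Protocol 5.2.3 applies that bar in every arm, and every arm starts with an adjuvanted 3.75 mcg dose. It gives no difference by interval.
- *A reader might infer that non-serious events are no longer recorded in subjects without dose 2.* Protocol 8.2.12 says "AEs will be limited to SAEs and MAAEs, including NOCMCs and PIMMCs, for subjects who are discontinued from receipt of the second study vaccination". Non-serious medically attended events, new-onset chronic conditions and potentially immune-mediated conditions are therefore still collected. The dilution does not depend on this, because none of these events can follow a dose that was not given.

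**Conclusion.** The point holds as a denominator error and an internal inconsistency. Post-dose-2 unsolicited AE incidence in Tables 102-103, and in the dose-2 files of Figures 30-31, is understated in relative terms by the share of the arm without dose 2. On the protocol's planning figures that is at most about 10% in the 4-month arms and 5% in the 21-day arms. In absolute terms it is 1.0 and 0.5 points at an assumed true 10%, rising to 5.0 and 2.5 points at 50%. The effect is zero if everyone receives dose 2.

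The sizes rest on two assumptions: the incidence values, which are mine, and the use of per-protocol exclusions as a ceiling for missed second doses. The existence of the error rests on neither. A bias between the two intervals is possible but not established. Displays without per-dose percentages, such as Tables 97-101, are not affected in this way.

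**What to change.** Add one sentence to SAP 9.3.2: for Post Vaccination 2 summaries, the denominator is the number of Safety Population subjects who received the second study vaccination. Change the footnotes of Tables 102 and 103, and the panel N and percentage base of the dose-2 files of Figures 30 and 31, to match. Keep the full Safety Population for Post Vaccination 1, since everyone in it had dose 1, and for Post Any Vaccination. Figures 28 and 29 plot event counts, so they need at most a changed N in the panel header.

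The cost is one sentence, the footnotes and a minor programming change. The SAP already uses dose-specific denominators for solicited events, and no data collection changes.

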3.2.2 Secondary

Safety:

- Occurrence of all unsolicited non-serious AEs from the time of each study vaccination through approximately 21 days after each study vaccination.
- Occurrence of all MAAEs, including NOCMCs and PIMMCs, from the time of the first study vaccination through approximately 12 months after the last study vaccination.

Immunogenicity:

- For HAI and Neut antibodies, percentage of subjects achieving seroconversion against the influenza A/H7N9 study vaccine viruses approximately 21 days after the first study vaccination as well as immediately prior to and approximately 180 days after the second study vaccination.
- For HAI and Neut antibodies, percentage of subjects achieving titer \geq 1:40 against the influenza A/H7N9 study vaccine viruses immediately prior to each study vaccination, approximately 21 days after the first study vaccination and approximately 180 days after the second study vaccination.

- GMTs of serum HAI and Neut antibodies against the influenza A/H7N9 study vaccine viruses immediately prior to each study vaccination, approximately 21 days after the first study vaccination and approximately 180 days after the second study vaccination.

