9 ASSESSMENT OF SAFETY

9.1 Specification of Safety Parameters

Safety will be assessed by the frequency and severity of:

1. SAEs occurring from the time of the first study vaccination through approximately 12 months after the last study vaccination.
2. Solicited AEs – reactogenicity events occurring from the time of each study vaccination through 7 days after each study vaccination:
 - a) Injection site reactions including pruritus, ecchymosis, erythema, induration (hardness)/edema (swelling), pain, and tenderness.
 - b) Systemic reactions including fever, feverishness, fatigue, malaise, myalgia, arthralgia, headache, and nausea.
3. Clinical safety laboratory AEs occurring from the time of each study vaccination through approximately 7 days after each study vaccination. Parameters to be evaluated include WBC, Hgb, PLT, ALT, T. Bili, Cr.
4. Unsolicited AEs –non-serious AEs occurring from the time of each study vaccination through approximately 21 days after each study vaccination.
5. MAAEs, including NOCMCs and PIMMCs, occurring from the time of the first study vaccination through approximately 12 months after the last study vaccination.

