11. TECHNICAL DETAILS

SAS version 9.4 or above will be used to generate all tables, figures and listings.

**12. SUMMARY OF CHANGES IN THE CONDUCT OF THE STUDY OR
PLANNED ANALYSES**

This SAP does not include any changes from the analyses described in the protocol.

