Table 103: Number and Percentage of Subjects Experiencing Non-Serious, Related Unsolicited Adverse Events Within 21 Days Post Study Vaccination by MedDRA® System Organ Class and Preferred Term, Vaccination and Study Group, Safety Population

| MedDRA® System Organ Class | MedDRA® Preferred Term | Post Vaccination 1 | | | | | | Post Vaccination 2 | | | | | | Post Any Vaccination | |
|--|------------------------|--------------------|----|----------|----|----------|----|--------------------|----|----------|----|----------|----|----------------------|----|
| | | Day 1-8 | | Day 9-22 | | Day 1-22 | | Day 1-8 | | Day 9-22 | | Day 1-22 | | Day 1-22 | |
| | | n | % | n | % | n | % | n | % | n | % | n | % | n | % |
| Group 1: 2013 3.75+AS03/ 2017 3.75+AS03 (D1-D22) (N=X) | | | | | | | | | | | | | | | |
| Any SOC | Any PT | x | xx | x | xx | x | xx | x | xx | x | xx | x | xx | x | xx |
| [SOC 1] | Any PT | x | xx | x | xx | x | xx | x | xx | x | xx | x | xx | x | xx |
| | [PT 1] | x | xx | x | xx | x | xx | x | xx | x | xx | x | xx | x | xx |
| | [PT 2] | x | xx | x | xx | x | xx | x | xx | x | xx | x | xx | x | xx |
| [SOC 2] | Any PT | x | xx | x | xx | x | xx | x | xx | x | xx | x | xx | x | xx |
| | [PT 1] | x | xx | x | xx | x | xx | x | xx | x | xx | x | xx | x | xx |
| | [PT 2] | x | xx | x | xx | x | xx | x | xx | x | xx | x | xx | x | xx |
| [Repeat for all study groups & All Subjects] | | | | | | | | | | | | | | | |
| N = Number of subjects in the Safety Population. This table presents number and percentage of subjects. For each time period, a subject is only counted once per PT. | | | | | | | | | | | | | | | |

[Implementation Note: If an SOC has only one PT reported, the ‘Any PT’ row will be omitted. Only the SOC/PT with >= 1 event reported will be shown for each group. Events through 'Day 22' include events through the study visit planned for 21 days post the relevant vaccination. If that visit is missed, then a cutoff of exactly 21 days post vaccination will be used.]

Table 104: Number of Unsolicited Adverse Events by MedDRA System Organ Class and Preferred Term, Day Post Study Vaccination, and Study Group, Safety Population

| MedDRA® System Organ Class | MedDRA® Preferred Term | Number of Events | | | | | | |
|---|------------------------|--------------------|----------|----------|--------------------|----------|----------|----------------------|
| | | Post Vaccination 1 | | | Post Vaccination 2 | | | Post Any Vaccination |

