16.2.7 Adverse Events

Listing 11: 16.2.7.1 - Solicited Events – Systemic Symptoms

| Subject ID | Study Group | Vaccination Number | Post Dose Day | Assessment ¹ | Symptom | Severity | Attributed to Alternate Etiology? ² | Alternate Etiology |
|------------|-------------|--------------------|---------------|-------------------------|---------|----------|--|--------------------|
| | | | | MA | | | | |
| | | | | Clinic | | | | |
| | | | | | | | | |
| | | | | | | | | |

¹ MA = Data reported by subject on the Memory Aid and reviewed by clinic staff and reported in Solicited Events eCRF.
Clinic = Data collected by clinic staff during physical exam or symptom assessment (treatment administration record, in-clinic assessment, etc.).
² Grade 3 events only.

Listing 12: 16.2.7.2 - Solicited Events – Local Symptoms

| Subject ID | Study Group | Vaccination Number | Product Received ¹ | Post Vaccination Day | Assessment ¹ | Symptom | Severity |
|------------|-------------|--------------------|-------------------------------|----------------------|-------------------------|---------|----------|
| | | | | | MA | | |
| | | | | | Clinic | | |
| | | | | | | | |
| | | | | | | | |

¹ MA = Data reported by subject on the Memory Aid and reviewed by clinic staff and reported in Solicited Events eCRF.
Clinic = Data collected by clinic staff during physical exam or symptom assessment (treatment administration record, in-clinic assessment, etc.).

Listing 13: 16.2.7.3 - Unsolicited Adverse Events

| Adverse Event | Associated with Vac # | # of Days Post Associated Vac (Duration) | Severity | SAE? MAAE? PIMMC? | Relationship to Study Vaccination | In Not Related, Alternative Etiology | Action Taken with Study Vaccination | Subject Discontinued Due to AE | Outcome | MedDRA® System Organ Class | MedDRA® Preferred Term |
|---|-----------------------|--|----------|-----------------------------------|-----------------------------------|--------------------------------------|-------------------------------------|--------------------------------|---------|----------------------------|------------------------|
| Subject ID: , Study Group: , AE Number: | | | | | | | | | | | |
| | | | | SAE: No MAAE: Yes PIMMC: No | | | | | | | |
| Comments: | | | | | | | | | | | |
| Subject ID: , Study Group: , AE Number: | | | | | | | | | | | |
| | | | | | | | | | | | |
| Comments: | | | | | | | | | | | |
| Note: For additional details about SAEs, see Section 14.3.3 . | | | | | | | | | | | |

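### SAP 9.3.2 restates the secondary safety endpoint as vaccine-related events only and assigns it the related-only Table 103, although Protocol 3.2.2 and SAP 3.2.2 say all events

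*SAP*

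**What the plan says.** Protocol 3.2.2 lists as a secondary safety outcome "Occurrence of all unsolicited non-serious AEs from the time of each study vaccination through approximately 21 days after each study vaccination". The Protocol Summary and SAP 3.2.2 use the same wording.

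SAP 9.3.2, in its list of unsolicited-AE displays, attaches a note to Table 103. The note says that this table presents the secondary safety endpoint, which it words as "Occurrence of study vaccine-related unsolicited non-serious AEs from the time of each study vaccination through approximately 21 days after each study vaccination". The Table 103 shell is titled "Number and Percentage of Subjects Experiencing Non-Serious, Related Unsolicited Adverse Events Within 21 Days Post Study Vaccination".

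SAP section 12 states: "This SAP does not include any changes from the analyses described in the protocol".

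**The concern.** One endpoint has two incompatible definitions inside the SAP, and the narrower one is tied to an output. A programmer or report author working from 9.3.2 would label Table 103 as the protocol's secondary safety endpoint. That figure would leave out every non-serious event judged not related.

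The filter also adds a step that the defined endpoint avoids. Relationship is judged by site physicians (Protocol 9.2.1), and site investigators know each subject's dosing interval (Protocol 5.2.2), which is one of the factors the trial compares. An endpoint covering all events does not depend on that judgement. A related-only endpoint does.

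**Working it through.** The main check is a comparison of texts. The documents state no figure to reproduce.

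**1. The endpoint wording.**
- Protocol Summary, Protocol 3.2.2 and SAP 3.2.2: *all* unsolicited non-serious AEs, about 21 days after each vaccination.
- Protocol 3.1.2 and SAP 3.1.2 (the matching objective): unsolicited non-serious AEs, with no relatedness limit.
- SAP 9.3.2: the same window and the same non-serious limit, but *study vaccine-related* in place of *all*.

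Only the 9.3.2 note differs.

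**2. The role of relationship in the protocol.** Protocol 11.6.2 plans counts and percentages of non-serious unsolicited AEs, broken down by severity and by relationship. Relationship is a dimension of the table, not an entry condition. Protocol 9.2.1 adds that the relationship assessment does not decide what is reported in the trial.

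**3. What the planned displays cover.** By title and shell, six of Tables 97 to 105 use the 21-day window:

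| Table | Relationship | Stated limit to non-serious |
|---|---|---|
| 99, 102, 104 | any | no |
| 101, 103, 105 | related only | yes |

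Tables 97, 98 and 100 have no 21-day limit in title or columns. Two other displays are explicitly non-serious and of any relationship, but neither is the full endpoint. Table 83 has a non-serious block, but it applies a 5% threshold and mixes in solicited and laboratory events. Table 110 lists only moderate or severe events.

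**4. Direction and size.** In one arm, let A be the number of subjects with at least one non-serious unsolicited AE in the window, and R the number with at least one such event judged related. Every subject in R is also in A, so R ≤ A and Table 103 cannot exceed the endpoint. With the planned 30 subjects per arm, the shortfall in the overall cell (any organ class, any vaccination) is (A − R)/30, or 1/30 = 3.3 percentage points per subject whose events were all judged not related. In narrower cells, by preferred term or by days 1–8 and 9–22, a subject with a related event elsewhere can also drop out. The documents give no expected values of A or R, so the shortfall cannot be estimated.

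**5. Whether Table 102 already is the endpoint.** Its title is "Number and Percentage of Subjects Experiencing Unsolicited Adverse Events Within 21 Days Post Study Vaccination", and it has columns for each vaccination and for either. Its scope depends on what an unsolicited AE is:
- Protocol 9.1, and SAP 4.5.1 in the same words, define unsolicited AEs as "non-serious AEs occurring from the time of each study vaccination through approximately 21 days after each study vaccination". On that reading Table 102 is the endpoint.
- SAP 9.3.2 describes Table 97 as covering "any unsolicited AE (serious or non-serious) for each MedDRA system organ class and preferred term over all study vaccinations" and says that all reported AEs enter the summaries. Listing 13, titled as unsolicited AEs, has a column headed "SAE? MAAE? PIMMC". On that reading Table 102 is the endpoint plus any SAEs in the window. The two coincide if there are none.

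**The case against.** The strongest reply is that this is a wrong explanatory note and nothing more. The section that defines endpoints, SAP 3.2.2, is correct. Unsolicited events of any relationship appear in Tables 97, 98, 99, 102 and 104, in Listing 13 and in several figures. Table 97 is in the topline set and Table 103 is not. If Table 102 does contain SAEs, these are listed individually in Table 106, and Protocol 11.6.2 expects few, so a careful reader could recover the endpoint.

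All of that stands, and it limits the point. A reader might infer from the 9.3.2 note that unrelated non-serious events would vanish from the report. The table shells do not support that: they are missing only from the table given the endpoint's label.

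A reader might also infer that no planned table shows the endpoint, because none of the any-relationship 21-day tables states a non-serious limit. That is not established either. Under SAP 4.5.1, Table 102 qualifies as it is. The contrast within 9.3.2 between AEs and non-serious, related AEs points the other way. The documents leave the matter ambiguous, which calls for clarification and not for a finding that Table 102 is wrong.

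The reply does not rescue the designation. Availability elsewhere does not make Table 103 the protocol's endpoint.

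**Conclusion.** The point holds as an error in the endpoint's wording and in its designated table. SAP 9.3.2 contradicts Protocol 3.2.2 and SAP 3.2.2, and section 12 gives no sign that a change was intended. The designated table would equal the endpoint only if filtering on relatedness removed no one from the counts. Otherwise it understates it, by an amount the documents do not allow to be estimated. The 3.3 points per subject is a unit of measure for one cell at 30 per arm, not a forecast.

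The conclusion rests on reading the definitions in the two 3.2.2 sections as governing. It does not depend on how the scope of Table 102 is resolved. That affects only which table should take over the designation.

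**What to change.** - In the SAP 9.3.2 note, replace *study vaccine-related* with *all*, and remove the statement that Table 103 presents the endpoint.
- Designate as the endpoint display a table in the Table 102 format: non-serious unsolicited AEs of any relationship, within about 21 days of each vaccination. If Table 102 is confirmed to exclude SAEs, use it. Otherwise add a non-serious version and leave the existing all-AE tables as they are, since 9.3.2 commits them to every reported event.
- Keep Table 103 as a supportive display.
- Give *unsolicited AE* one meaning in SAP 4.5.1 and 9.3.2, stating whether SAEs are included.
- If a related-only endpoint was intended, declare it in section 12 with the reason.

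The cost is a corrected note, one aligned definition and at most one added table from an existing shell. No new data are needed: Listing 13 already carries the SAE flag, the relationship and the days since vaccination.
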